3.2. Violations and Deviation

Subjects who do not meet eligibility criteria but are still randomized will be analyzed according to the analysis sets described in Section 3.1.

Major protocol deviations are considered to have major impact on subject safety, efficacy or the validity of the study data.

Patients with major efficacy protocol deviations will be excluded from the PPS and PPS-I under the assumption that the deviation may have an impact on the efficacy analysis, and from PPS-UES under the assumption that the deviation may have an impact on the urodynamics analysis. This may include, but is not limited to the following:

- Subjects who do not meet the following inclusion criteria:
 - On a stable dose of alpha blocker
 - Average frequency of ≥ 8 and ≤ 20 micturitions per day in the baseline diary
 - Average frequency of ≥ 3 urgency episodes per day in the baseline diary
 - Average frequency of ≥ 2 nocturia episodes per night in the baseline diary
- Subjects who meet any of the following exclusion criteria:
 - Total 24-hour urine volume output of >3000 mL based on any baseline diary day
 - History of prostate surgery
 - Subject started using diuretics within 28 days prior to screening
 - Nocturnal Polyuria ($> 1/3$ of total urine output per 24 hours occurring at nighttime) assessed on any day of the baseline diary
 - Has received an intravesical or intraprostatic treatment with any botulinum toxin, resiniferatoxin, or capsaicin within 6 months prior to screening
 - Use of any prohibited anticholinergics or beta-3 adrenergic agonists as detailed in protocol section 10.6 within 28 days prior to screening
- Concomitant use of prohibited medications as detailed in protocol section 10.6
- $<70\%$ Investigational Product [IP] compliance from Baseline through Week 12
- Visit delay at or prior to Week 12 causing more than 14 days without IP
- Failed to complete any diary day for an expected Week 12 diary within Study Day 68-102 [PPS and PPS-I only]

Exclusion from per-protocol analysis is noted for each protocol deviation in the Protocol Deviation specifications.

The final list of major protocol deviations will be finalized and documented before database lock except for the deviation of wrong treatment which will be confirmed upon study unblinding. All major protocol deviations related to efficacy will be finalized prior to unblinding. Only major protocol deviations will be summarized and listed in the Clinical Study Report (CSR).

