4.3.3. Study Day and Duration

Study day is relative to the start date of the double-blind treatment. This is used to describe the relative time of an event or assessment that happened during the study. The first day of the study is defined as the day a patient first receives either vibegron or placebo in the double-blind treatment period. This is expected to be the same day as the randomization as Day 1. There is no study Day 0 defined in the study.

- For event or assessment occurring on or after the first dose of double-blind treatment date:
Study day = Date of event or examination – date of first double-blind treatment + 1
- For event or assessment occurring prior to the first dose of double-blind treatment date:
Study day = Date of event or examination – date of first double-blind treatment

A duration between any two dates (such as AE duration) expressed in days will be calculated using the following convention:

- Duration = Later date – earlier date + 1

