5.9. Treatment Exposure

The duration of exposure during the double-blind treatment period will be expressed as the time in days from the first dose as recorded on the Study Drug Administration CRF page through to last treatment day (inclusive) as recorded on the End of Treatment CRF page, excluding any days where it is recorded that an interruption has occurred on the AE CRF page or gaps in the study drug log. If no dose was witnessed at the baseline visit, the date of baseline study drug dispensation + 1 will be used. If no last treatment date is recorded, it will be imputed as the minimum of the date of the last visit on the study and the date when last dispensed study treatment was scheduled to be exhausted (last dispensation date + number of doses dispensed).

Gaps in the study drug log will be determined by comparing the dispensation date of a record to the previous dispensation date (where multiple bottles may have been dispensed). If one bottle was dispensed, then the gap is measured from study day of previous dispensation + 32; if two bottles were dispensed then the gap is measured from study day of previous dispensation + total number of pills dispensed.

Interruption in days = date interruption stated – date interruption stopped + 1

The duration is calculated by the following formula:

Duration (days) = date last double blind dose – date first double blind dose – interruption days + 1

Duration of exposure will be summarized by treatment group and overall for the SAF using summary statistics for continuous variables. Total drug interruption days due to AE and gaps in the study drug log will also be summarized. A listing will present the treatment start and end date together with the date of interruption, and the overall duration of exposure.

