5.10. Treatment Compliance

Study treatment compliance (%) will be calculated as the actual number of doses divided by the expected number of doses, multiplied by 100 and summarized by treatment group and double-blind treatment period.

These numbers will be determined by the number of tablets dispensed and returned unused by the subject. Where no treatment bottle is returned, and thus the actual number of doses is

unknown, it will be assumed that the subject took medication as directed until their supply was exhausted. Imputed values will be clearly noted in the listing.

The expected number of doses is the same as the calculated duration of exposure detailed in section 7.1.

Overall compliance will be calculated for run-in and the double-blind treatment period, respectively.

$$\text{Overall Compliance (\%)} = \frac{\text{Number of doses taken}}{\text{Expected number of doses}} \times 100\%$$

The number of doses taken is summed from values recorded on the drug accountability CRF. If number of doses taken is missing for a log line within the drug accountability CRF, it will be imputed as the minimum of (number of doses dispensed, subsequent dispensation date – current dispensation date).

Treatment Compliance will be summarized for the SAF and FAS population. Additionally, the number and percentage of subjects within each treatment with compliance in the following categories will be provided: <80%, 80 – 120%, and >120%. All data will be listed.

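### The SAP 5.9 interruption formula has its dates reversed, so any interruption of 3 days or more, if coded as printed, is added to exposure and understates compliance

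*SAP*

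**What the plan says.** SAP 5.9 (Treatment Exposure) describes exposure as the days from first to last double-blind dose, "excluding any days where it is recorded that an interruption has occurred on the AE CRF page or gaps in the study drug log". It then gives two formulas: "Interruption in days = date interruption stated – date interruption stopped + 1", and "Duration (days) = date last double blind dose – date first double blind dose – interruption days + 1". It also asks for a summary of total interruption days.

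SAP 4.3.3 (Study Day and Duration) gives the general convention for days between two dates: "Duration = Later date – earlier date + 1".

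SAP 5.10 (Treatment Compliance) defines compliance as doses taken over expected doses and says: "The expected number of doses is the same as the calculated duration of exposure detailed in section 7.1". Section 7.1 is Adverse Events; exposure is in 5.9. On the periods covered, 5.10 says: "Overall compliance will be calculated for run-in and the double-blind treatment period, respectively". It also reports compliance in three categories, the lowest being below 80%.

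SAP 3.2 (Violations and Deviation) lists among the per-protocol exclusions a value under 70% for "Investigational Product [IP] compliance from Baseline through Week 12".

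**The concern.** Reading the word printed as 'stated' as 'started', the interruption line takes the start date minus the stop date. The result is negative for all but the shortest interruptions. Because the duration formula subtracts it, the days that 5.9 means to remove are added instead.

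The error would pass through three outputs: the exposure table, the interruption-day summary, and compliance, whose denominator is exposure. It might also reach per-protocol membership through the 70% rule. A programmer who follows the cross-reference in 5.10 to Section 7.1 finds no exposure formula there to check against. Interruptions are foreseen: Protocol 8.4.6.1 provides for temporary withholding of study drug with possible rechallenge, and SAP 5.9 expects interruptions to be recorded on the adverse event page.

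**Working it through.** The documents state no exposure or compliance result, so there is no figure of the plan's own to reproduce. The check is date arithmetic.

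**Inputs**
- Formulas: SAP 5.9 and 5.10.
- Full period T = 168 days, from 24 weeks of once-daily dosing (Protocol 1.1).
- Baseline to Week 12 taken as T = 84 days. This is an assumption, because the SAP does not define the period for compliance.
- Adherence outside the interruption: 100%, 90% or 80%. These are assumptions for illustration.

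**Interruption days.** For an interruption of L days, stop = start + L − 1.
- As printed: start − stop + 1 = 2 − L.
- As intended: stop − start + 1 = L.
- So L = 1 gives 1 (correct), L = 2 gives 0, L = 3 gives −1, L = 10 gives −8 and L = 20 gives −18.

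**Exposure.** Duration = T − interruption days.
- As printed: T − (2 − L). As intended: T − L. The overstatement is 2L − 2 days.
- T = 168, L = 10: 168 − (−8) = 176, against 168 − 10 = 158. The difference is 18 = 2 × 10 − 2.
- Exposure exceeds the calendar span only from L = 3.

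**Compliance over the double-blind period.** Doses taken = adherence × (T − L), divided by the duration. With full adherence outside the interruption and T = 168:
- L = 10: 158/176 = 89.8%, against 158/158 = 100% as intended.
- L = 20: 148/186 = 79.6%, in the category below 80%, against 148/148 = 100%.

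**The 70% rule, if it uses the same formula with T = 84**

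| Adherence outside interruption | L (days) | As printed | As intended |
|---|---|---|---|
| 100% | 15 | 69/97 = 71.1% | 100% |
| 100% | 16 | 68/98 = 69.4% | 100% |
| 90% | 12 | 0.90 × 72/94 = 68.9% | 90% |
| 80% | 7 | 0.80 × 77/89 = 69.2% | 80% |

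The values 16, 12 and 7 are the shortest interruptions that cross 70% at each adherence level. If the rule used the full 168 days, a fully adherent man would cross it only at 31 days (137/197 = 69.5%).

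**The case against.** The strongest reply is that this is a transposition and the plan already shows the intended direction twice, in the opening sentence of 5.9 and in 4.3.3. The error would also tend to show itself: the required summary of interruption days would include negative values, and SAP 2.2 calls for blinded dry runs before database lock. This stands as a reason to expect that the error would be caught. It does not make the printed rule right, and a programmer or validator who follows the specific formula gets wrong numbers.

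Four stronger readings are tempting, and the documents do not support them.

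- A reader might infer that every interruption lengthens exposure. It does so only from 3 days. Nor is it shown that the reversal reaches gaps in the drug log, which have their own derivation in 5.9 from dispensation dates and tablet counts.
- A reader might infer that men will be wrongly excluded from the per-protocol set. That is conditional. SAP 5.10 gives no formula for compliance from Baseline to Week 12. SAP 3.2 refers to deviation specifications that are not part of these documents, and 3.1.7 settles membership at a blinded review. SAP 3.2 also has a separate exclusion for visit delays leaving more than 14 days without drug, so any added effect falls mainly on interruptions for adverse events.
- A reader might infer that netting interruptions out of expected doses is itself an error, because a long interruption then never lowers compliance. With the dates corrected, a man with a 28-day interruption who takes the other 56 doses shows 56/56 = 100%, against 56/84 = 66.7% on calendar days. But 5.9 and 5.10 net these days out deliberately, and the protocol itself provides for withholding drug. A calendar-day denominator would newly exclude an otherwise fully adherent man with a 26-day interruption (58/84 = 69.0%). Reasonable statisticians would differ, so this is a design choice.
- A reader might infer that the co-primary result is at risk. The full analysis set (SAP 3.1.6) has no compliance criterion, and the per-protocol analysis is supportive.

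**Conclusion.** The interruption formula in SAP 5.9 is wrong as printed and contradicts both its own section and 4.3.3. This part rests on no assumption. Coded literally, it overstates exposure by 2L − 2 days for an interruption of L days, makes the interruption-day summary wrong for any interruption longer than 1 day, and understates compliance. The wrong cross-reference in 5.10 is also certain.

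The effect on the per-protocol set is possible but not established. It requires literal coding and use of the same formula for the 70% rule. The thresholds of about 16, 12 and 7 days further assume an 84-day window and adherence of 100%, 90% and 80% outside the interruption. The documents give no frequency of interruptions, so the number of men affected is unknown. The co-primary inference and the testing hierarchy are untouched. The error is bounded and checkable, and should be corrected because exposure and compliance are reported results.

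**What to change.** Three edits to the SAP:

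1. In 5.9, define interruption days as the stop date minus the start date, plus 1, and correct 'stated' to 'started'.
2. In 5.10, change the cross-reference for expected doses from 7.1 to 5.9.
3. In 5.10, state that the compliance from Baseline to Week 12 used in 3.2 takes as expected doses the corrected 5.9 exposure truncated at Week 12, with doses taken counted over the same days.

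The plan's choice to leave interrupted days out of expected doses stays as it is. The cost is one formula, one reference and one sentence, with no new data. Because per-protocol membership is fixed before unblinding, the edits belong before that point. If the SAP is already final, Section 1 of the SAP provides for recording the change in the clinical study report.

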5.10. Treatment Compliance

Study treatment compliance (%) will be calculated as the actual number of doses divided by the expected number of doses, multiplied by 100 and summarized by treatment group and double-blind treatment period.

These numbers will be determined by the number of tablets dispensed and returned unused by the subject. Where no treatment bottle is returned, and thus the actual number of doses is

unknown, it will be assumed that the subject took medication as directed until their supply was exhausted. Imputed values will be clearly noted in the listing.

The expected number of doses is the same as the calculated duration of exposure detailed in section 7.1.

Overall compliance will be calculated for run-in and the double-blind treatment period, respectively.

$$\text{Overall Compliance (\%)} = \frac{\text{Number of doses taken}}{\text{Expected number of doses}} \times 100\%$$

The number of doses taken is summed from values recorded on the drug accountability CRF. If number of doses taken is missing for a log line within the drug accountability CRF, it will be imputed as the minimum of (number of doses dispensed, subsequent dispensation date – current dispensation date).

Treatment Compliance will be summarized for the SAF and FAS population. Additionally, the number and percentage of subjects within each treatment with compliance in the following categories will be provided: <80%, 80 – 120%, and >120%. All data will be listed.

6. EFFICACY ANALYSIS

Subjects were asked to fill out a Bladder Diary for 3 consecutive days prior to the Run-in visit, Baseline visit, and at Weeks 2, 4, 8, 12, 16, 20, and 24.

In general, the FAS will be used for all analyses of efficacy endpoints except for incontinence efficacy endpoints where the FAS-I will be used.

All outputs that present a CFB will also present descriptive statistics on the baseline value of the parameter.

6.1. Co-Primary Endpoint Analysis

6.1.1. Primary Analysis

The primary analysis will be based on the FAS. Descriptive summary for observed and CFB will be provided by visit and treatment for both co-primary endpoints. Refer to parameter derivations from Bladder Diary data on Section 4.3.1.

Co-primary 1: CFB to Week 12 in average number of daily micturition episodes

For the assessment of difference between the treatment groups in change from baseline to Week 12 in average number of daily micturition episodes, a mixed model for repeated measures (MMRM) will be used incorporating on-treatment values at all time points (Weeks 2, 4, 8, 12, 16, 20, and 24). The model takes account of any correlation within the same subject over time by using all available data on the subjects. With the assumption of missing at random (MAR), this approach will provide unbiased estimates of treatment effects derived from the model.

The MMRM model will include terms for treatment, visit, baseline value (average number of daily micturition episodes), alpha blocker use with or without 5-ARI (with vs. without), baseline urinary incontinence (yes vs. no), region (US vs. non-US), and interaction of visit by treatment. Stratification factors as randomized will be used in the model. The Kenward-Roger adjustment will be used with restricted (or residual) maximum likelihood (REML) to make statistical inference. An unstructured covariance matrix will be used to model the correlation among repeated measurements. If the unstructured covariance model fails to converge with the default Newton-Raphson algorithm, the Fisher scoring algorithm will be used to provide initial values of the covariance parameters. In the rare event that none of the above methods yield convergence, the following structures will be investigated: heterogeneous Toeplitz, Toeplitz, heterogeneous First-Order Autoregressive [AR (1)], heterogeneous compound symmetry (HCS), and compound symmetry (CS). The covariance structure converging to the best fit, as determined by Akaike's information criterion (AIC), will be used.

Primary inference will be drawn from the treatment difference between vibegron and placebo at Week 12. Results will be presented in terms of least square means (LSMEANS), treatment differences in LSMEANS, 95% confidence intervals for the treatment difference for all timepoints. Although nominal p-values for the treatment differences will be presented for all visits, the primary inference is at Week 12. The estimated LSMEANS (Standard Error (SE)) of CFB over time from the model will be plotted by treatment.

An example of the SAS code for the base procedure is given below:

```
proc mixed data = datain method = reml;
  class TRTP AVISITN USUBJID ALPHAB UI REGION;
  model CHG = TRTP AVISITN ALPHAB UI REGION BASE TRTP*AVISITN
    / ddfm=KR solution chisq;
  repeated AVISITN / subject=USUBJID type=UN r rcorr;
  lsmeans TRTP*AVISITN / pdiff=all cl alpha=0.05;
run;
```

Where TRTP is the planned treatment, AVISITN is the visit number, USUBJID is the unique subject identifier, ALPHAB indicates if the subject used 5-ARI in addition to alpha blockers at baseline, UI indicates baseline urinary incontinence, REGION indicates if the subject is in the United States or in the non-US countries and BASE indicates baseline value. The default Newton-Raphson algorithm is employed for type = UN. If the default algorithm fails to converge, use Fisher scoring algorithm to include option scoring = 5 in the model.

The normality assumptions for the primary analysis model will be assessed by inspection of the residuals from the model and normal probability plots. If assumptions of normality are not met, additional supportive analysis of the data will be performed in order to assess the robustness of the conclusions drawn from the primary analysis.

Co-primary 2: CFB to Week 12 average number of daily urgency episodes

The primary analysis will be identical to the analyses specified for the first co-primary described above with the addition of fitting in the categorical covariate of baseline average number of daily micturition episodes (≤ 12 vs. > 12 , stratification factor as randomized).

Multiplicity of Co-Primary Endpoints

No multiplicity adjustment is required for the co-primary endpoints since both endpoints need to be statistically significant at the 0.05 level in order to claim trial success.

6.1.2. Sensitivity Analysis

6.1.2.1. Per-Protocol Analysis

To assess the robustness of the results from primary analysis, the same MMRM models will be conducted to both co-primary endpoints based on PPS.

6.1.2.2. Analysis of Covariance with Multiple Imputed data

An ANCOVA model will be used as a sensitivity analysis. For patients with missing Week 12 assessment due to any reason, the Week 12 value will be imputed using multiple imputation (see Appendix 11.1 for further details). The model will include terms for treatment, baseline value of the parameter, region (US vs. non-US), and stratification factors as randomized: alpha blocker use (with vs. without 5-ARI), baseline urinary incontinence (yes vs. no), baseline number of average daily micturition episodes (≤ 12 vs. > 12 , only included for the urgency parameter). The analysis will be performed on FAS and PP analysis sets.

An example of the SAS code for the base procedure is given below:

```
proc mixed data = datain method = reml;
  class TRTP ALPHAB UI REGION;
  model CHG = TRTP AVISITN ALPHAB UI REGION BASE
    / ddfm=KR solution chisq;
  Where AVISIT = "Week 12";
  lsmeans TRTP/ pdiff cl alpha=0.05;
run;
```

A tipping point analysis will accompany the multiply imputed ANCOVA results, and the estimated shift parameter will be presented to two decimal places.

The normality assumptions for the ANCOVA analysis model will be assessed by inspection of the residuals from the model and normal probability plots. If assumptions of normality are not met, additional supportive analysis of the data will be performed in order to assess the robustness of the conclusions drawn from the primary analysis.

This supportive analysis will use the multiple imputation (MI) data at Week 12 using a non-parametric analysis of covariance within the framework of the extended Cochran-Mantel-Haenszel test. Specifically, a Cochran-Mantel Haenszel mean score test will be used on the standardized mid-ranks of the residuals from an ordinary least squares regression with Week 12 MI response as a linear function of the baseline score (as a continuous variable). P-value for the between treatment comparison for each primary endpoint will be derived for the model.

This methodology will be carried out as follows:

1. The observed value of the primary endpoint (i.e., the last on treatment average number of daily micturition episodes) will be fitted using an ordinary least squares regression as a function of the baseline value at each visit
2. Standardized mid-ranks of the residuals from the regression will be calculated.
3. The standardized mid-rank from the last observation will be carried forward for missing values at week 12
4. Standardized mid-ranks will be recalculated
5. A CMH mean score statistic and p-value adjusting for the stratification groupings will be calculated for between treatment comparisons

An example of the SAS code for the base procedure is given below:

```

proc glm Data=datain;
  by Avisitn;
  model aval = Base;
  output out=glmout residual=Residual;
run;

proc rank data=glmout out=Rank1 nplus1 ties=mean;
  by Avisitn;
  var Residual;
  ranks RANKOBS;
run;

proc sort data=rank1;
  by subject avisitn;
run;

data rankmi;
  set rank1;
  by subject avisitn;
  if last.subject;
run;

proc rank data=rankmi out=ADRANK nplus1 ties=mean;
  by avisitn;
  var RANKOBS;
  ranks Rankana;
run;

proc freq data = ADRANK;
  tables stratified vars*TRTP*Rankana / cmh2 scores = table;
run;

```

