3.1.3. Randomized Set

The Randomized Set consists of all subjects who are randomized to receive any double-blind study medication regardless of whether they took a dose or not.

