3.1.6. Full Analysis Set

The Full Analysis Set (FAS) population will serve as the primary population for the analysis of efficacy data in this trial. Since the endpoints related to incontinence only apply to subjects who meet the definition of incontinence at trial entry, it is necessary to have a separate FAS definition with an additional criterion to define the primary analysis population for incontinence endpoints.

The following FAS populations are defined in the study:

- **Full Analysis Set (FAS):** consists of all randomized subjects who took at least one dose of double-blind study medication and have at least one evaluable change from baseline micturition measurement. Subjects will be analyzed according to their randomized treatment, irrespective of premature discontinuation, according to the Intent-to-Treat principle.
- **Full Analysis Set for Incontinence (FAS-I):** consists of all randomized subjects with incontinence at baseline (as calculated from the baseline diary) who took at least one dose of double-blind study treatment and have at least one evaluable change from baseline urinary incontinence measurement.

Note that “subjects with urinary incontinence at baseline” are defined as meeting the following criteria based on the 3-day bladder diary completed by the subject during the Run-in period:

- An average of ≥ 8.0 micturitions per Diary Day. A “Diary Day” is defined as the time between when the subject gets up for the day each morning (i.e., the time the subject got up for the day yesterday to the time the subject got up for the day today; approximately a 24-hour period).
- An average of ≥ 1.0 urinary incontinence episodes per Diary Day

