3.1.7. Per-Protocol Set

The Per-Protocol Set (PPS) and Per-Protocol Set for Incontinence (PPS-I) exclude patients from the FAS and FAS-I due to important deviations from the protocol that may substantially affect the results of the efficacy endpoints (i.e., Major PDs associated with efficacy). The Per-Protocol set for Urodynamics (PPS-UES) exclude subjects from UES due to important deviations from the protocol that may substantially affect the results of the urodynamics endpoints. A supportive analysis using the PPS and PPS-I will be performed for the co-primary and secondary efficacy endpoints, and a supportive analysis using the PPS-UES will be performed for the primary urodynamics parameters (Qmax and PdetQmax). The final determination on protocol deviations, and thereby the composition of the Per-Protocol Sets, will be made prior to the unblinding of the database and will be documented per the Protocol Deviation Plan during the blinded data review

meeting. Subjects will be included in the treatment group to which they are randomized, regardless of which treatment was actually received, for the analyses of efficacy data using the PPS and PPS-I.

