11.1. Appendix 1. Multiple Imputation for the Response Efficacy Endpoints

This section summarizes the multiple imputation approach for the sensitivity analysis of primary efficacy endpoints to assess the robustness of the treatment effect under different underlying assumptions to account for missing data. The goal is to impute missing values as follows:

- Average number of daily micturition episodes
- Average number of daily urgency episodes

First the average daily numbers will be derived for all post-baseline visits as described in Section 4.3.1 respectively, then the following two-stage imputation will be applied. The following steps will be followed to perform this analysis.

Step 1: Create a horizontal dataset for the efficacy data where each patient has 1 row per parameter and a column for each visit from baseline through week 12, inclusive.

Step 2: Impute missing average daily numbers at Weeks 2, 4, and 8 based on MCMC to obtain a monotone missing data pattern with 30 replicates. Example code is:

```
proc mi data = datain1 out = dataout1 seed = 123 n impute=30 n o print;
  var baseline WEEK_02 WEEK_04 WEEK_08;
  mcmc chain = multiple impute=monotone;
  em maxiter = 1000;
run;
```

Step 3: For each of the 30 replicates from Stage 1, impute the missing data following a monotone missing data pattern so that there are 30 replicates of the complete dataset. Example code is:

```
proc mi data = dataout1 out = dataout2 seed = 321 n impute=1 n o print;
  class TRTP OABTYPE REGION ;
  monotone regression (WEEK_12 = baseline WEEK_02 WEEK_04 WEEK_08);
  var WEEK_12 baseline WEEK_02 WEEK_04 WEEK_08;
run;
```

Step 4: Transpose the dataset out2 to the usual ADaM-like dataset with 1 row per patient, per parameter, per analysis visit.

Step 5: Fit the ANCOVA model from Section 6.1.1 for each of the replicate complete datasets.

Step 6: Combine the results from Step 4 using PROC MIANALYZE.

```
proc mianalyze data = MIdatain;
  modeleffects ESTIMATE;
```

```
stderr STDERR;
ods output ParameterEstimates = MIout;
run;
```

The tipping point analysis will use the same approach and follow Example 80.13 from SAS/STAT User's Guide [8].

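### The imputation and tipping-point check of the co-primaries omits randomised men with no post-baseline diary, and its printed steps do not give the monotone pattern they rely on

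*SAP*

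**What the plan says.** The sensitivity analysis in SAP 6.1.2.2 imputes missing Week 12 values and fits an ANCOVA, accompanied by a tipping-point analysis. Its scope is stated in one line: "The analysis will be performed on FAS and PP analysis sets".

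- **FAS (SAP 3.1.6):** "all randomized subjects who took at least one dose of double-blind study medication and have at least one evaluable change from baseline micturition measurement".
- **PPS (SAP 3.1.7 and 3.2):** the per-protocol sets "exclude patients from the FAS and FAS-I due to important deviations from the protocol", so the PPS lies inside the FAS. One listed ground for exclusion is "Failed to complete any diary day for an expected Week 12 diary within Study Day 68-102".
- **Randomized Set (SAP 3.1.3):** this holds everyone randomised, "regardless of whether they took a dose or not". No missing-data analysis of the co-primaries uses it.

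SAP Appendix 11.1 gives the imputation. The dataset has "a column for each visit from baseline through week 12, inclusive". Step 2 reads: "Impute missing average daily numbers at Weeks 2, 4, and 8 based on MCMC to obtain a monotone missing data pattern". Step 3 regresses Week 12 on baseline and Weeks 2, 4 and 8, and its variable list puts Week 12 first. Treatment is declared as a class variable but appears in neither the variable list nor the regression. The tipping point follows the same approach. The primary MMRM in SAP 6.1.1 uses Weeks 2 to 24.

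**The concern.** A tipping-point analysis asks how bad the unseen outcomes would have to be before the result is lost. Here the men with the least data are left out of that question. The first diary window opens on Day 7 (SAP 4.2.4.2). A man who leaves earlier without a usable diary is in no planned efficacy analysis, although the FAS is described as following intent-to-treat. Such losses need not be balanced between arms: stopping drug also means leaving the study (Protocol 7.2), and the listed reasons for stopping include urinary retention (Protocol 7.1). These men could be imputed, because eligibility requires three consecutive diary days in the run-in (Protocol 8.2.1).

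Separately, a two-stage imputation works only if its first stage leaves a monotone pattern for the second. The printed steps do not ensure that.

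**Working it through.** **1. The plan's own figures.** SAP 1.2.4 gives 544 per arm, 15% lost by Week 12, 462 evaluable per arm, effects of 0.46 and 0.60, and SDs of 1.972 and 2.811.
- 544 × 0.85 = 462.4, so 924 in total and 1088 − 924 = 164 men without a Week 12 value.
- Micturition: SE = 1.972 × √(2/462) = 0.1297. 0.46/0.1297 = 3.545, and Φ(3.545 − 1.96) = 94.4% (94.3% with the t distribution).
- Urgency: SE = 2.811 × √(2/462) = 0.1850. 0.60/0.1850 = 3.244, and Φ(3.244 − 1.96) = 90.0%.

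The stated 94.3% and 90% reproduce.

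**2. Who is stressed.** Let q be the share of randomised men with no post-baseline diary. It is not in the documents; I take 1% to 3%. Then 11, 22 or 33 of 1088 men fall outside the FAS, and it imputes 164 − 11 = 153, 142 or 131 men instead of 164.

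**3. Tipping shift.** Assume the planned effect is observed, the shift is applied to imputed vibegron values only, and the SE stays at its 462-per-arm value (imputation adds no information). A shift δ on an imputed share f of the arm moves the arm mean by fδ, so the result tips at

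δ = (d − 1.96 × SE) / f.

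On all randomised men f = 0.15. On the FAS f = (0.15 − q)/(1 − q). The numerators are 0.46 − 0.2543 = 0.2057 and 0.60 − 0.3625 = 0.2375.

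| Set | f | Micturition δ | Urgency δ |
|---|---|---|---|
| All randomised | 0.1500 | 1.37 | 1.58 |
| FAS, q = 1% | 0.1414 | 1.45 | 1.68 |
| FAS, q = 2% | 0.1327 | 1.55 | 1.79 |
| FAS, q = 3% | 0.1237 | 1.66 | 1.92 |

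Using 82/544 instead of 15% gives 1.36, then 1.45, 1.54 and 1.65 for micturition. The ratio of FAS to all-randomised shift is 0.15(1 − q)/(0.15 − q), that is 1.06, 1.13 and 1.21. It does not depend on the effect or the SD.

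**4. Monotone pattern.** A pattern is monotone for an ordered list if, once a value is missing, all later ones are missing.
- *Step 2.* Take a man with Weeks 2 and 4 observed, Week 8 missing and Week 12 observed. On Step 2's list (baseline to Week 8) he is already monotone, so nothing needs filling. Once Week 12 is added he is not monotone.
- *Step 3.* With Week 12 listed first, every man who lacks Week 12 but has a baseline value breaks the order. Those are the men to be imputed.

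**5. Treatment term.** With no treatment term, a man with only a baseline diary is imputed without regard to arm. Adding a share q of such men multiplies the expected difference by 1 − q: 0.46 × 0.97 = 0.446 at q = 3%. An all-randomised run under the printed model would mix this dilution with the effect of the missing data.

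**The case against.** The FAS is prespecified and is defined identically in Protocol 9.3. Early losses are not hidden: SAP 5.1 tabulates inclusion in each set, and reasons for exclusion, by arm on the Randomized Set. An early leaver can still enter the FAS if his withdrawal diary falls in a visit window within 21 days of his last dose (SAP 4.2.4.2). Protocol 2.3.1 reports adverse-event discontinuation below 5% in all earlier vibegron studies, so the 3% end of the range is probably high. At roughly three to three and a half times the planned effect, any of these shifts would read as reassuring. All of this stands, and it limits the size of the point. A table of exclusions does not, however, show what those men would do to the result.

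On the code, the SAP calls it an example and plans blinded dry runs (SAP 2.2), so a failure should surface before unblinding. But the omission of Week 12 is in the wording of Step 2 as well as in its code.

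Three stronger readings are tempting and unsupported.
- *The treatment estimate is biased by a known amount.* That needs an excess early loss and an outcome gap, and the documents give neither. Under missing-at-random imputation, baseline-only men change little; the omission matters in the tipping point.
- *Ignoring Weeks 16 to 24 costs material precision.* Under one assumed correlation structure, those visits cut the residual variance of an imputed Week 12 value from 0.464 to 0.375 (as a share of the Week 12 variance). If 2% to 5% of men are affected (assumed), the variance of the contrast changes by about f/(1 − f) × 0.089, or 0.2% to 0.5%, and its SE by under 0.3%. Few men may qualify, since Protocol 8.6 sends those who cannot attend Week 12 to an early-withdrawal visit.
- *Men with later diaries should escape the shift.* Their Week 12 value is still missing, and SAP 6.1.2.2 imputes it whatever the reason. Exempting them would make the check less conservative.

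**Conclusion.** The point holds as a limited defect in a sensitivity analysis. Randomised men with no evaluable post-baseline diary are never imputed or stressed, so the reported shift overstates robustness by about 6% to 21% if 1% to 3% of men are in that position. This rests on the assumed rates, the planning effects and SDs, and a shift applied to vibegron only. The direction follows from the set definitions; the size will be known only from the data. The per-protocol run cannot fill the gap, because the PPS is a subset of the FAS and can also drop men who missed an expected Week 12 diary.

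The printed imputation scheme needs correction whatever the early-loss rate. The primary MMRM and its inference at Week 12 are untouched.

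**What to change.** 1. In SAP 6.1.2.2, add a supplementary imputation ANCOVA and tipping point on all randomised men with a baseline diary, and keep the FAS version beside it. State this as an exception to SAP 4.2.3, which only lists the data of untreated men. For never-dosed men, count study days from randomisation, since SAP 4.3.3 counts from first dose.
2. In Appendix 11.1, carry columns to Week 24, include Week 12 and Weeks 16 to 24 in the Step 2 imputation, and order the variable list from baseline to last visit.
3. Impute by treatment arm, or put treatment in the imputation model. Without this, item 1 would dilute the difference.
4. Keep the tipping shift on every imputed Week 12 value, and state to which arm it applies.

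The cost is SAP wording, a little more programming and one extra supportive table per endpoint. No new data are needed.
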